6 STUDY ENROLLMENT AND WITHDRAWAL

A total of three hundred (300) Subjects will be enrolled in the study, from a maximum of fifty (50) community practices (sites) from across the U.S. During the study enrollment window, study-eligible clinical sites will be sequentially screened, consented for study participation and completion of all study procedures, including enrollment of study eligible Subjects.

The study Subjects will be patients diagnosed with AK on the face or scalp, and aged 18 years or above at the time of initiation of treatment. The study cohort will be drawn from dermatology clinics from across the U.S.

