6.4.1 Reasons for Withdrawal

Subjects are free to withdraw from participation in the study at any time upon request.

A Site Investigator may terminate a study Subject's participation in the study if:

- Any medical condition, event or situation occurs such that continued participation in the study would not be in the best interest of the Subject. This may include pregnancy among female Subjects, per clinician judgment.
- The Subject meets a study exclusion criterion (either newly developed or not previously recognized) that precludes further study participation.
- The Site Investigator or the study coordinator is unable to reach the Subject and the Subject is considered as lost to follow-up.

6.4.2 *Handling of Subject Withdrawals*

If a Subject requests withdrawal from the study voluntarily for any reason, the Site Investigators or site coordinator will follow-up with the patient to solicit and document the reason for withdrawal, unless the Subject is considered as lost to follow-up. If the Site Investigator determines that the withdrawal is related to an adverse drug reaction (ADR) or serious adverse event (SAE) associated with tirbanibulin, he/she will gather necessary information concerning the ADR/SAE. The Site Investigator may follow-up with the subject subsequently to ensure resolution of ADR/SAE episode and close out the study documentation for the concerned Subject. There will be no replacement of Subjects who withdraw or discontinue early from the study.

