6.2 Analysis Populations and Datasets

Statistical analysis and data tabulation will be performed using the following analysis populations unless specified otherwise:

- Safety Population: All patients who received at least one dose of tirbanibulin during the study observation period of 8-weeks related to primary endpoint, as part of usual care.
- Full Analysis Set (FAS): All patients within the Safety Population that had at least some data pertaining to the key variables studied at relevant timepoints, post-baseline.

All safety evaluations (part of additional objectives) will be conducted among the safety population, while FAS will be used to conduct analyses addressing rest of the study objectives, including the primary objective.

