7 DATA TABLES

All patients who received at least one dose of tirbanibulin during the study observation period and had at least some data pertaining to study primary endpoints (PROs) at Week 8 will be included in **Full Analysis Set (FAS)** to facilitate the planned descriptive analysis.

Correspondingly, patients who completed the study survey at Week 8 will be included in FAS, since patients answering Week 8 survey will have completed all relevant PRO related questions.

Safety data analyses will be conducted among the **Safety Population**, that correspond to the entire study cohort that took at least one dose of tirbanibulin. Correspondingly, all patients completing the baseline survey and took at least one dose of tirbanibulin, amounting to N=300 will be included in this analysis.

Section 7.1 Patient Demographics, Perceptions & PROs (FAS Population)

Table 1.1 Population	25
Table 1.2 Patient Demographic Characteristics	26
Table 1.3 Patient Self-Assessment: AK Treatment Motivators.....	28
Table 1.4 Patient Self-Assessment: Baseline Skin Texture.....	28
Table 1.5 Patient Reported Medication Compliance.....	29
Table 1.6 SKINDEX-16: Patient Response Summary.....	30
Table 1.7 SKINDEX-16: CFB at Week-8 for Individual Items.....	36
Table 1.8 SKINDEX-16: Domain Scores.....	41
Table 1.9 Subgroup Analysis of SKINDEX-16 Domain Scores.....	42
Table 1.10 Patient Evaluation of Overall Appearance in the Original Treated Area.....	43
Table 1.11 Subgroup Analysis of Patient Evaluation of Overall Appearance in the Original Treated Area	44
Table 1.12 Treatment Satisfaction Questionnaire for Medication (TSQM-9): Patient Scores in the Original Treated Area.....	46
Table 1.13 Subgroup Analysis of TSQM-9 Patient Domain Scores	47
Table 1.14 Patient Satisfaction with Tirbanibulin in the Original Treated Area (looks/texture)	48
Table 1.15 Subgroup Analysis of Patient Satisfaction with Treatment Ability to Improve How Skin Looks in the Original Treated Area	49
Table 1.16 Subgroup Analysis of Patient Satisfaction with Treatment Ability to Improve Skin Texture in the Original Treated Area ..	51
Table 1.17 Patient Relative Satisfaction of Tirbanibulin in Comparison with Other Topical Medications for AK in the Original Treated Area	53
Table 1.18 Subgroup Analysis of Patient Relative Satisfaction of Tirbanibulin, Regarding Duration of Skin Reactions	56
Table 1.19 Subgroup Analysis of Patient Relative Satisfaction of Tirbanibulin, Regarding Severity of Skin Reactions	58

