Table 1.4 Patient Self-Assessment: Baseline Skin Texture

Skin Texture *	Baseline (N=x)
S13 If you run your hand across your face and/or scalp, how would you describe the texture:	
S13r1 Dry	n (%)
S13r2 Smooth	n (%)
S13r3 Rough	n (%)
S13r4 Bumpy	n (%)
S13r5 Scaly	n (%)
S13r6 Blistering	n (%)
S13r7 Peeling	n (%)

Note: *Mutually exclusive Data from Patient DCF; X patients had missing data; The denominator for the percentage is the number of patients with available data (N=XX)

Table 1.5 Patient Reported Medication Compliance

Character	Week 8 (N=X)
MC1: Did you take all five doses as prescribed?	
Yes	n (%)
No	n (%)
MC2: If no, how many doses did you miss (out of five total)?	
None [^]	n (%)
One	n (%)
Two	n (%)
Three	n (%)
Four	n (%)
Five	n (%)

Note: Data from Patient DCF. [^]None corresponds to MC1=Yes; all other responses corresponds to MC1>No.

Table 1.6 SKINDEX-16: Patient Response Summary

Domain	Baseline (N=X)	Week 8 (N=X)
Symptoms		
SK1: Over the past week, how often have you been bothered by itching?	n Mean (SD), Median,Min,Max	n Mean (SD), Median,Min,Max
Never Bothered (0)	n (%)	n (%)
(1)	n (%)	n (%)
(2)	n (%)	n (%)
(3)	n (%)	n (%)
(4)	n (%)	n (%)
(5)	n (%)	n (%)
Always Bothered (6)	n (%)	n (%)
Symptoms		
SK2: Over the past week, how often have you been bothered by Burning or Stinging?	n Mean (SD), Median,Min,Max	n Mean (SD), Median,Min,Max
Never Bothered (0)	n (%)	n (%)
(1)	n (%)	n (%)
(2)	n (%)	n (%)
(3)	n (%)	n (%)
(4)	n (%)	n (%)
(5)	n (%)	n (%)
Always Bothered (6)	n (%)	n (%)
Symptoms		
SK3: Over the past week, how often have you been bothered by your skin condition hurting?	n Mean (SD), Median,Min,Max	n Mean (SD), Median,Min,Max
Never Bothered(0)	n (%)	n (%)
(1)	n (%)	n (%)
(2)	n (%)	n (%)
(3)	n (%)	n (%)

(4)	n (%)	n (%)
(5)	n (%)	n (%)
Always Bothered (6)	n (%)	n (%)
Symptoms		
SK4: Over the past week, how often have you been bothered by your skin condition being irritated?	n Mean (SD), Median,Min,Max	n Mean (SD), Median,Min,Max
Never Bothered(0)	n (%)	n (%)
(1)	n (%)	n (%)
(2)	n (%)	n (%)
(3)	n (%)	n (%)
(4)	n (%)	n (%)
(5)	n (%)	n (%)
Always Bothered (6)	n (%)	n (%)
Emotions		
SK5: Over the past week, how often have you been bothered by persistence/recurrence of skin condition?	n Mean (SD), Median,Min,Max	n Mean (SD), Median,Min,Max
Never Bothered(0)	n (%)	n (%)
(1)	n (%)	n (%)
(2)	n (%)	n (%)
(3)	n (%)	n (%)
(4)	n (%)	n (%)
(5)	n (%)	n (%)
Always Bothered (6)	n (%)	n (%)
Emotions		

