7.4 Tables from Clinician DCF: Safety Data Analysis

These analyses will use Safety Population dataset.

All patients who started the study and received at least one dose of the sarecycline during the study observation period, as part of usual care. This corresponds to the entire cohort of 300 eligible patients who started the study.

Table 4.1 Safety Analysis Population

S1: Population	N=x
Total FAS Population	n (%)
Total Safety Population	n (100%)

Note: Data from Patient DCF

Table 4.2 Study Subject Selection Criteria, Safety Population

Domain (N=X)	Yes	No
SS1r1 Diagnosed with actinic keratoses of the face and/or scalp?	n (%)	n (%)
SS1r2 Has clinically typical, visible, and discrete AK lesions?	n (%)	n (%)
SS1r3 Considered a candidate for tirbanibulin (Klisyri®) AND you plan to administer tirbanibulin (Klisyri®) treatment?	n (%)	n (%)
SS1r4 At least 18 years of age at the time of initiation of tirbanibulin (Klisyri®) treatment?	n (%)	n (%)
SS1r5 Willing to avoid excessive sun or UV exposure, and/or use relevant sunscreen protection and protective clothing during the study duration.	n (%)	n (%)
SS1r6 Able to read and write English.	n (%)	n (%)
SS1r7 Able to provide consent to participate AND is willing to comply with study procedure?	n (%)	n (%)
SS2r1 Have another dermatological condition of the face that could interfere with the actinic keratoses clinical evaluations?	n (%)	n (%)
SS2r2 Hypertrophic AK lesions, open wounds or suspected skin cancers within close proximity of the treatment area	n (%)	n (%)
SS2r3 Anticipated need for in-patient hospitalization or in-patient surgery within the next 2 months.	n (%)	n (%)
SS2r4 Have a medical chart accessible to complete baseline data collection?	n (%)	n (%)

Note: Data from Clinician DCF. The denominator for the percentage is the number of patients with available data (N=X). There are no missing data.

Table 4.3 Patient Demographic Characteristics, Safety Population

Adult Demographic Data	Total (N=x)
S1: Age	Mean, SE (SD) Median Min, Max
S3: Gender	
Male	n (%)
Female	n (%)
Other S3r3oe	n (%)
S4: Marital Status	
Not Married	n (%)
Not Marries, living with Partner	n (%)
Married or Civil Union	n (%)
Divorced or Separated	n (%)
Widow/Widower	n (%)
Prefer not to answer	n (%)
S5: Highest level of Education	
Less than high school diploma/degree	n (%)
High school degree or equivalent (e.g., GED)	n (%)
Some college but not degree	n (%)
Associated degree	n (%)
Bachelor's degree	n (%)
Graduate degree	n (%)

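### SAP Sections 7 and 7.4 restate the Safety Population differently from its one-dose definition and assert N=300 instead of deriving it from dosing evidence

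*SAP*

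**What the plan says.** SAP 6.2 defines the set as "All patients who received at least one dose of tirbanibulin during the study observation period of 8-weeks related to primary endpoint", and Protocol 12.2 uses the same rule. Neither mentions a survey or gives a number.

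SAP 7 repeats the one-dose condition but describes the set as "all patients completing the baseline survey and took at least one dose of tirbanibulin, amounting to N=300".

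SAP 7.4 gives a third description: "All patients who started the study and received at least one dose of the sarecycline during the study observation period". It then adds: "This corresponds to the entire cohort of 300 eligible patients who started the study".

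Tables 4.29 and 4.30 (other safety events) carry N=300 in the column header. Table 4.11 (disposition) shows 300 at each visit, labelled as the total study population.

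The figure matches the enrolment target in Protocol 6: "A total of three hundred (300) Subjects will be enrolled in the study". Under Protocol 6.4.2, "There will be no replacement of Subjects who withdraw or discontinue early from the study".

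**The concern.** A safety denominator should come from one rule applied to the data. Here a programmer has three descriptions that need not select the same patients, and a total that equals the recruitment target.

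Two errors become possible, of different kinds. An enrolled patient who never applied the ointment cannot have a drug reaction or a local skin reaction to it. Counting that patient lowers the reported rates. Conversely, a patient who was dosed but has no baseline survey belongs in the set under SAP 6.2 and falls out of it under SAP 7, along with any events.

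The sarecycline wording cannot be applied at all, because that is not the study drug. SAP 7.4 therefore needs rewriting in any case.

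**Working it through.** **Step 1. Compare the definitions.**

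| Place | Dosing condition | Survey condition | Size stated |
|---|---|---|---|
| Protocol 12.2 | One dose of tirbanibulin | No | No |
| SAP 6.2 | One dose of tirbanibulin | No | No |
| SAP 7 | One dose of tirbanibulin | Baseline survey completed | 300 |
| SAP 7.4 | One dose of sarecycline | No | 300, everyone who started |

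**Step 2. Try to reproduce 300.** Let u be the number enrolled but never dosed. Enrolment is 300 (Protocol 6) and withdrawals are not replaced (Protocol 6.4.2), so:

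Safety N = 300 − u

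This equals 300 only when u = 0. Neither document gives u or a count of dosed patients, so 300 can be neither derived nor refuted.

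**Step 3. Ask whether u could exceed zero.**
- Baseline may fall up to 2 weeks before the index date, and the index date is only the planned first application (Protocol 7; SAP 4).
- The first application may be made at home (Protocol 5).
- Patients may withdraw at any time after enrolment (Protocol 6.4).
- The missed-dose item MC2 in Table 1.5 accepts five of five.

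None of this shows an undosed patient. It shows that being enrolled does not establish being dosed. If each enrolled patient independently had probability q of never being dosed, then P(at least one undosed among 300) = 1 − (1 − q)^300. For assumed q of 0.1%, 0.5%, 1% and 2%, this is 26%, 78%, 95% and 99.8%.

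**Step 4. Size the effect of a fixed 300.** Printed rate = true rate among dosed × (300 − u)/300. For a true rate of 10%, with assumed values of u:

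| u (share of 300) | Factor | Printed rate |
|---|---|---|
| 0 (0%) | 300/300 = 1.00 | 10.0% |
| 6 (2%) | 294/300 = 0.98 | 9.8% |
| 15 (5%) | 285/300 = 0.95 | 9.5% |
| 30 (10%) | 270/300 = 0.90 | 9.0% |

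**Step 5. Check where 300 is actually used.** Among the safety summaries, only Tables 4.29 and 4.30 print it. Table 4.1, the local reaction table (4.13) and the AE and ADR summaries (4.15 to 4.23 and 4.25 to 4.27) leave N open. The text of Sections 7 and 7.4 still governs what will fill those cells.

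**Step 6. Check the survey condition.** Table 4.11 has a row for missing surveys with a baseline patient-survey column, so the SAP itself allows for missing baseline surveys. The baseline window runs to 7 days after the index date and the course lasts 5 days, so a patient could finish treatment before baseline is due. How many would be affected is not given, and the direction of the effect depends on whether those patients had events.

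**The case against.** A reader might infer that the SAP contradicts the one-dose rule and orders undosed patients into every safety percentage. The documents do not support that. Sections 7 and 7.4 both keep a one-dose condition, and no passage tells anyone to include an undosed patient. The sentence in Section 7 is most plainly read as asserting that 300 patients meet the rule.

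The figure may also be a known count. Parts of the SAP are written in the past tense, and Table 4.2 already notes that no data are missing. Some of that may be carried over from a template (Section 7.4 names the wrong drug), so it does not settle the matter.

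Three further points stand:
- Most safety tables leave N open.
- Table 4.11 is a disposition table, for which enrolled patients are a proper base.
- Table 1.5 is a Full Analysis Set table, and that set already requires a dose, so its five-missed option is weak evidence.

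A simple repair, accepting as dosed only patients confirmed by MC1/MC2 or by clinician item P2, would do harm. These are Week 8 items. P2 asks whether the 5-day course was completed, so a negative answer does not separate no doses from some. A patient who applied the drug and left early, perhaps because of a drug reaction, could have neither item and would be removed from safety.

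What the objection leaves untouched is the added survey condition, the wrong drug name, the whole-cohort equation and a preset denominator with no stated source.

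**Conclusion.** The point holds as an inconsistency in the population definition together with an underived denominator. The SAP should not fix the Safety Population at the enrolment target unless it can cite dosing evidence that all 300 were treated.

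Dilution is conditional. It is zero if everyone was dosed. Under the assumed 2% to 10% undosed, it is 0.2 to 1.0 percentage points on a true 10% rate, wherever 300 is the denominator. Both the undosed share and the 10% rate are assumptions. The effect of the survey condition cannot be sized from the documents.

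The study is descriptive and nothing here threatens its main conclusions. The correction is still worth making before lock, because the same definition underlies all the AE, ADR and local reaction percentages.

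**What to change.** - In SAP 7 and 7.4, restore the SAP 6.2 rule. Delete the baseline-survey condition, the sarecycline wording and the equation with the whole cohort.
- Replace N=300 in both sections and in Tables 4.29 and 4.30 with a count derived from dosing evidence. If 300 proves to be that count, cite its source.
- Keep 300 in Table 4.11 if it is the actual enrolment, and add a row for patients with no dose.
- Count a patient as dosed on any record of application: a supervised first dose where the site recorded one; MC1 = Yes, or MC2 below five; P2 = Yes; or a treatment-emergent local reaction, ADR or treatment discontinuation. Table 4.13 has a baseline column, so a local reaction should count only if its onset follows the start of treatment.
- Exclude only patients documented as never dosed. List those with unknown dosing separately, and show the safety rates with and without them.

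The cost is revised SAP wording, a derivation rule that draws on several forms instead of one item, an extra disposition row and a second set of safety percentages. No new data collection is proposed. Patients whose records are silent on dosing go into the unknown group. Some rates may rise slightly.

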5 STUDY MEDICATION

The study protocol will require identification and selection of patients considered as candidates for a specific medication, namely, tirbanibulin (Klisyri®), as part of usual care. In this context, the study medication will be tirbanibulin (Klisyri®). Clinicians at individual sites (referred to as ‘Site Investigators’) shall provide the commercial supply of tirbanibulin (Klisyri®) to eligible study Subjects.

Tirbanibulin has an evolving market access in the U.S, with payers reimbursing for the commercial prescriptions on a restricted basis. Selection of only the patients who are able to fill the prescription for reimbursed tirbanibulin may not be representative of individuals who might be candidates for tirbanibulin in the U.S; this may impact the generalization of the study results. To avoid this potential selection bias and improve the prospect of generalization of study results, the commercial supply of tirbanibulin (Klisyri®) will be supplied to Site Investigators for the 5-day treatment episode for each of their Subjects.

Per FDA prescribing information, the recommended dosage of Klisyri® (tirbanibulin ointment 1%) is 1 single-dose packet (2.5 mg tirbanibulin in 250 mg) per application, for 5 consecutive days. The Site Investigators will prescribe tirbanibulin to patients per their clinical judgement. Correspondingly, tirbanibulin prescribed dose and frequency will be captured as part of study data collection.

The first dose of tirbanibulin may be administered by the subject at the clinic (under the supervision of study personnel, at baseline encounter), or at subject's home. Following the first application, Subjects will self-administer the remaining single-dose packets once daily at home for the next 4 consecutive days. Study medication should be applied each day at approximately the same time. It is preferable that study drug application is done early in the day. Subjects will be advised so that the treatment area is not touched or made wet for approximately 12 hours after application.

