4 STUDY SCHEDULE & PROCEDURES

Study eligible patients who are considered as candidates for tirbanibulin treatment as part of usual care AK management will be screened, consented, and recruited into the study, followed for up to 24 weeks post-index date, encompassing three distinct data collection encounters. With 'T' being the index date of tirbanibulin treatment initiation, the baseline data collection (from both Site Investigators and Subjects) may transpire anytime between T= -2 weeks post-index date and T= +7 days post-index date; the 8-week follow-up data collection (Study Encounter # 2; from both Site Investigators and Subjects) will happen at T=8 weeks post-index date \pm 7 days; and 24-week follow-up data collection (Study Encounter #3; from both Site Investigators and Subjects) will happen at T=24 weeks post-index date \pm 14 days. Index date is the planned date of first application/initiation of tirbanibulin treatment, after the subject was prescribed the tirbanibulin. Different data elements will be collected from Site Investigators and from study Subjects at these data collection encounters, as outlined below.

The schedule of events is summarized in Appendix A.

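### SAP 7 and 7.4 contradict the one-dose Safety Population rule of SAP 6.2: Section 7 adds a baseline-survey condition and a preset N of 300; Section 7.4 names the wrong drug and equates the set with all 300 starters

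*SAP*

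**What the plan says.** Three places in the SAP describe the Safety Population.

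- **SAP 6.2**, matching protocol 12.2: "All patients who received at least one dose of tirbanibulin during the study observation period of 8-weeks related to primary endpoint". There is no survey condition and no fixed number. The same section assigns all safety evaluations to this population.
- **SAP 7**, before the list of tables: the first sentence on this population agrees with 6.2 in requiring a dose. The second, offered as a consequence of the first, reads "all patients completing the baseline survey and took at least one dose of tirbanibulin, amounting to N=300 will be included in this analysis".
- **SAP 7.4**, directly above the safety tables: patients who started the study and "received at least one dose of the sarecycline during the study observation period". It continues: "This corresponds to the entire cohort of 300 eligible patients who started the study".

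Nothing says which description governs. Tables 4.29 and 4.30 print N=300 as their base, although SAP 6.1 gives the planned sample only as approximately 300.

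**The concern.** A safety denominator should be fixed by exposure to the drug. Section 7 also makes it depend on completing a questionnaire. A patient who applied the ointment, reacted and never completed the baseline survey counts under 6.2 but is lost under the second sentence of Section 7, and the reaction is lost too. If such patients react more often than others, the reported rates are too low.

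Section 7.4 has a different fault. It names a drug that this study does not supply, and it declares the set identical to everyone who started, before any count of dosed patients is shown. A programmer working from the text directly above the safety tables meets a wrong drug name and a ready-made denominator.

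Safety and tolerability is a stated additional objective, so the population behind these tables should be unambiguous.

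**Working it through.** **Side by side**

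| Place | Dose required | Survey required | Size stated |
|---|---|---|---|
| SAP 6.2, protocol 12.2 | Tirbanibulin, within 8 weeks | No | None |
| SAP 7, first sentence | Tirbanibulin | No | None |
| SAP 7, second sentence | Tirbanibulin | Baseline survey | 300 |
| SAP 7.4, first sentence | Sarecycline | No | None |
| SAP 7.4, second sentence | Not mentioned | No | 300 (all starters) |

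**When the wordings agree.** Read sarecycline as tirbanibulin. Let E be the patients who started, D those dosed, and S those with a baseline survey. Section 6.2 selects D, the second sentence of Section 7 selects D∩S, and the second sentence of 7.4 names E. Since D∩S lies within D, and D within E, the three are the same set only if every starter was both dosed and surveyed. The figure of 300 cannot be reproduced from any inputs: SAP 6.1 states that no formal calculation was made.

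**Can they differ in this design?**

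- *Dosed but not surveyed.* Baseline data collection "may transpire anytime between T= -2 weeks post-index date and T= +7 days post-index date". A 5-day course begun on the index date can be over before that window closes. Table 4.11 has a row for missing surveys, with baseline columns.
- *Started but not dosed.* "Index date is the planned date of first application/initiation of tirbanibulin treatment", and baseline may come 2 weeks before it. Protocol 5 allows the first dose at the clinic "under the supervision of study personnel, at baseline encounter), or at subject's home". Protocol 6.4.2 does not replace withdrawals.

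Both are possible. The documents do not show that either occurred.

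**Size of the survey condition (assumed counts).** Take 300 dosed patients, b of them without a baseline survey, and 10 severe local skin reactions (LSRs) among the surveyed. Section 7 prints 10/(300−b). The all-dosed rate lies between 10/300 (none of the b reacted severely) and (10+b)/300 (all did).

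| b | Section 7 prints | All-dosed, lowest | All-dosed, highest |
|---|---|---|---|
| 3 | 10/297 = 3.4% | 10/300 = 3.3% | 13/300 = 4.3% |
| 5 | 10/295 = 3.4% | 10/300 = 3.3% | 15/300 = 5.0% |
| 9 | 10/291 = 3.4% | 10/300 = 3.3% | 19/300 = 6.3% |

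For a common outcome the effect is slight. With b = 5 and 236 surveyed patients having any LSR, Section 7 prints 236/295 = 80.0%, against 236/300 = 78.7% to 241/300 = 80.3%.

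**Size of a preset base of 300 (assumed counts).** If 0%, 1% or 5% of 300 starters were never dosed, the 6.2 denominator is 300, 297 or 285. Thirty subjects with an event are then 10.0%, 10.1% or 10.5%, where a base fixed at 300 always gives 10.0%.

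**The case against.** The strongest reply is that 300 is a count and not a target. Parts of the SAP read as if written with the study under way: some text is in the past tense, a 2022 drug dictionary is cited, a specific site is named, and Table 4.11 prints 300 as the total in every column. At face value, Sections 7 and 7.4 together say that surveyed and dosed equals 300 equals everyone who started, and then nothing changes. This is inference, but it stands as a real possibility.

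It is also fair that sarecycline looks like text carried over from another study. A reference to a PROSES study (Table 2.1), an acne-medication row (Tables 2.31 and 4.9) and a week-12 clinician dataset (SAP 7.3) look the same. Most safety tables print N=X, so only 4.29 and 4.30 fix the base at 300. Protocol 7.1 expects baseline data at enrolment or shortly after, which makes a dosed patient without a survey less likely.

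Two stronger readings are tempting, and the documents do not support them.

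- A reader might infer that 7.4 admits patients who never applied the drug. Its first sentence requires a dose. The all-starters sentence describes the result of that rule and does not replace it.
- A reader might infer that undosed patients can enter the FAS, because "patients who completed the study survey at Week 8 will be included in FAS" and Table 1.5 has a row for five missed doses out of five. The preceding sentence in SAP 7 requires a dose for the FAS, and a response option does not show that anyone chose it.

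None of this removes the survey condition, the wrong drug name or the preset number from the operative text.

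**Conclusion.** The inconsistency is real. All the wordings that state a rule require a dose, but the second sentence of Section 7 adds a condition that 6.2 and protocol 12.2 do not contain. Section 7.4 names the wrong drug and asserts an identity with all starters that depends on every starter having been dosed.

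The expected numerical effect is small for common reactions, and zero if all 300 were dosed and surveyed. It could be proportionately larger for rare or severe events, but only if some dosed patients lack the survey and react more often than the rest; the documents are silent on both. The percentages above rest on assumed counts. Severity: minor, a correction of consistency and drafting that leaves the study's design and primary analysis untouched.

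**What to change.** 1. Apply the SAP 6.2 rule wherever the Safety Population is described.
2. In SAP 7, delete the baseline-survey condition and the stated total of 300.
3. In SAP 7.4, replace sarecycline with tirbanibulin and delete the sentence equating the population with the 300 starters.
4. In Tables 4.29 and 4.30, replace N=300 with the actual number dosed. In Table 4.30, which counts events, show both events and subjects.
5. In Table 4.1, show the numbers enrolled, dosed, and not dosed or of unknown dosing status.

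The last line of Table 4.1 is needed because the existing items do not settle dosing for everyone. The missed-dose question (MC2) is available only from Week 8 survey respondents, and clinician question P2 asks whether the 5-day course was completed, so a negative answer does not establish that no dose was taken.

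The cost is a few lines of SAP text, two table headers and one extended table, with no new data collection. The downside is that the Safety Population may differ from 300 and cannot be printed in advance.
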